
• Prior kidney transplantation• Congenital or iatrogenic absence of one kidney• Subjects on renal replacement therapy at the time of OLT• MELD score >34• HIV positive patient• Patient with current severe systemic infection• History of bacterial peritonitis within 30 days prior to OLT• Active infection or recent infection within 30 days prior to OLT• Use of a calcineurin inhibitor continuously for more than 90 days within the past 6 months• History of hypersensitivity to Thymoglobulin®, rabbits or tacrolimus• Pregnant and/or nursing (lactating) females.• Women of childbearing age who are unwilling to use effective contraception during the duration of the study, and for 30 days after study participation and/or last dose of Study Drug.
STUDY MEDICATION (DOSE/ROUTE/REGIMEN): Subjects randomized to the (Delay CNI) group will be treated with Thymoglobulin® (total dose of 4.5 mg/kg) administered in three doses; (each dose being 1.5 mg/kg – administered Day 0 [after transplant], Day 2, and Day 4 post transplant), along with CNI delay for 10 days. CNI will be initiated on postoperative (post-transplant) Day 10. Subjects will also receive a maintenance immunosuppression regimen of corticosteroids and MMF in accordance with the standard practice at each clinical center.
REFERENCE MEDICATION (DOSE/ROUTE/REGIMEN): Subjects randomized to the (Early CNI) group (Control group) will receive no antibody therapy for induction and will start CNI therapy on postoperative (post-transplant) Day 2. Subjects will also receive a maintenance immunosuppression regimen of corticosteroids and MMF in accordance with the standard practice at each clinical center.

STUDY SYNOPSIS: (continued)

PRIMARY ENDPOINT(s):

- The incidence of AKI at 30 days post-transplant.
- Serum creatinine and eGFR at 30 days post-transplant

SECONDARY ENDPOINT(s):

- The incidences of acute cellular rejection, (ACR), at 30 days post-transplant.
- Patient survival at 6 months post-transplant.
- Graft survival at 6 months post-transplant.
- Incidence of AEs and SAEs

ABBREVIATIONS AND TERMS:

ACE	angiotensin converting enzyme
ACR	acute cellular rejection
ADQI	acute dialysis quality initiative
AE	adverse event
AKI	acute kidney injury
AKIN	acute kidney injury network
ALT	alanine aminotransferase
ARF	abnormal renal function
AST	aspartate aminotransferase
ATN	acute tubular necrosis
AUC	area under the curve
BCG	Bacillus Calmette-Guerin (vaccine)

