An overview of the safety profile of Thymoglobulin® is presented. The most common systemic AEs during and after Thymoglobulin® infusion are: fever (63%), chills (57%), pain (46%), headache (40%), abdominal pain (38%), diarrhea (37%), hypertension (37%), nausea (37%), peripheral edema (34%), dyspnea (28%), asthenia (27%), hyperkalemia (27%), and tachycardia (27%), (*Thymoglobulin® Prescribing Information*). Hypotension, vomiting, and malaise have also been commonly reported. The likely mechanism of action for these events is the release of cytokines during the first dose administration, particularly if appropriate premedications were not administered. Localized AEs, such as pain at the infusion site and peripheral thrombophlebitis, have also been reported. Rare delayed allergic reactions such as serum sickness, (fever, pruritus, and rash associated with joint and muscle pain), may occur 7 to 15 days post-treatment initiation. Immediate serious allergic reactions and/or anaphylaxis are very rare.

AEs associated with the presence of antibodies inducing cross-reactions such as leucopenia (57%) and thrombocytopenia (37%) have been reported during and after treatment with Thymoglobulin®, (*Thymoglobulin® Prescribing Information*). These reactions may emerge during the first 2 days of treatment or after treatment. The mechanism of action likely causing these effects involves the presence of antibodies cross-reacting with shared antigens of lymphocytes, neutrophils, and platelets, or additive effects from concomitant medication. Monitoring of the WBC and platelet counts enables the severity and frequency of such reactions to be reduced.

AEs associated with over-immunosuppression, including infectious complications (bacterial, fungal, viral, and/or protozoal), and malignancies, (particularly lymphoproliferative syndrome), have been reported. It is important to note that concomitant or previous immunosuppressive treatments may contribute to over-immunosuppression. Appropriate anti-infective prophylaxis will significantly reduce the incidence of infections and possibly the incidence of viral-associated malignancies.

STUDY OBJECTIVES:

A. Primary Objective:

- To determine if a 10 day delayed introduction of CNI reduces the risk/incidence of perioperative acute kidney injury, (AKI), and long-term renal dysfunction in patients undergoing liver transplantation.

B. Secondary Objective(s):

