Mycophenolate mofetile	1000 mg BID start on day one post-transplant	1000 mg BID start on day one post-transplant
Corticosteroids	As per Transplant Center Immunosuppression Protocol - Taper off between 21 days-6 months post LT	As per Transplant Center Immunosuppression Protocol - Taper off between 21 days-6 months post LT

The Data Safety Monitoring Board (DSMB) will review the data on the first 30 subjects who have completed 30 days study enrollment.

Primary Endpoints:

- The incidence of AKI at 30 days post-transplant.
- Serum creatinine and eGFR at 30 days post-transplant.

Secondary Endpoints:

- The incidences of acute cellular rejection, (ACR), at 30 days post-transplant.
- Patient survival at 6 months post-transplant.
- Graft survival at 6 months post-transplant.
- The incidences of AEs and SAEs.

The primary endpoint for the study is a composite renal endpoint of Acute Kidney Injury, (**stages 2 to 3**), at 30 days post OLT. The staging of AKI will follow the classification system proposed by the Acute Kidney Injury Network (AKIN) depicted in **Table 2**.²⁶

TABLE 2: Classification / Staging for Acute Kidney Injury (AKI)

Classification/Staging System for Acute Kidney Injury ²⁶		
Stage:	Serum Creatinine Criteria	Urine Output Criteria:
1	Increase in serum creatinine of ≥ 0.3 mg/dL, (≥ 26.4 $\mu\text{mol/L}$), or an increase of $\geq 150\%$ to 200% , (1.5 to 2-fold), from baseline.	Less than 0.5 mL/kg per hour for more than 6 hours
2	Increase in serum creatinine of $> 200\%$ to 300% , (>2 to 3-fold), from baseline.	Less than 0.5 mL/kg per hour for more than 12 hours
3 ^a	Increase in serum creatinine to more than 300% , (>3 -fold), from baseline, (or serum creatinine of ≥ 4 mg/dL, [≥ 354 μmol], with an acute increase of ≥ 0.5 mg/dL, [44 $\mu\text{mol/L}$].	Less than 0.3 mL/kg per hour for 24 hours, or anuria for 12 hours.

^aOnly **one criterion** (creatinine or urine output) must be fulfilled to qualify for a stage. Individuals receiving renal replacement therapy (RRT) are considered to have met the criteria for **Stage 3** irrespective of the stage they were in at the time of RRT.

B. Patient Population

Study participants will be recruited from the Liver Transplant Programs at Cleveland Clinic, Cleveland, Ohio; University of Cincinnati, Cincinnati, Ohio; Medical College of Wisconsin Milwaukee, Wisconsin, and Cleveland Clinic Weston, Florida

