from the study. Information will be collected on serum creatinine levels, urea, eGFR, rejection episodes, graft loss/re-transplant, malignancies, opportunistic infections, patient survival and immunosuppressive therapy.

Subjects who did not complete the planned Thymoglobulin® course will be followed for any SAE(s) occurring within 30 days following the last dose of Thymoglobulin®. **These SAE(s) will be reported on the (MedWatch SAE Form) and UPLOADED to the Sanofi PV Portal, and faxed to Cleveland Clinic PI – “Attention: [name]” at [contact], within 24 hours of Study Site discovery/notification.** Since subjects will be followed even after discontinuation of the Study Drug, the **Study Completion CRF** should only be completed at 30 days, and Month 12 or earlier if the subject can no longer be followed. The following reasons are potential causes for premature discontinuation of study: graft loss, death, lost to follow-up and withdrawal of consent.

I. Emergency Un-Blinding of Treatment Assignment

This is an open-label study.

J. Study Completion and Post-Study Treatment

A Study Completion CRF should be completed at Month 12. The Investigator also must provide follow-up medical care for all patients who are prematurely withdrawn from the study, or must refer them for appropriate ongoing care. In addition, investigators will be asked to provide, for each randomized patient, a one-year follow-up data to describe patient survival, graft survival, acute rejection, current immunosuppressive regimen, recurrence of hepatitis C and renal function.

EFFICACY AND SAFETY ASSESSMENTS:

A. Renal function

Renal function will be assessed by estimated Glomerular Filtration Rate (eGFR), using the MDRD 4-variable equation. Serum creatinine will also be used as a parameter for determination of renal function at each Study Visit. Subjects will be classified for each occurrence of AKI according to the criteria in **Table 2**. Serum creatinine and weight must be recorded on the Study Visit CRF. All subjects will have their eGFR assessed at baseline, **Month 1, 3, 6, 9 and Month 12 post-transplant.**

B. Acute Cellular Rejection

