Designated Study Personnel, (at each Study Site), must enter the information required by the protocol onto the paper Case Report Forms (CRFs). The information from the paper CRFs will then be entered directly into the electronic Database, REDCAP, by designated Study personnel at each Study Site. Edit checks and double data entry with verification upon second entry are built

into specific data items. Text items (e.g. comments) are entered once. Queries are sent to the investigational site using an electronic data query. Designated investigational Study Site staff will be required to respond to all queries and make any necessary changes to the data. Other errors or omissions are entered on Data Query Forms, which are made accessible to the investigational site for resolution.

Concomitant medications entered into the database will be coded using the WHO Drug Reference List which employs the Anatomical Therapeutic Chemical classification system. Coexistent diseases and Adverse Events (AEs) will be coded using the Medical dictionary for regulatory activities (MedDRA) terminology.

D. Handling of Missing Values/Censoring/Discontinuations

Since the study subjects will be followed for renal function, graft loss, or survival status, the subjects with missing measurements at 30 days will only be those who die, withdraw consent or are lost to follow-up. It is expected there will be very few such patients within 30 days. Missing values at day 30 will be imputed using the last observation carried forward (LOCF) approach. Missing baseline serum creatinine values will be replaced with the most recent available value from the pre-transplant period.

STUDY ENDPOINTS / EFFICACY AND SAFETY

A. Primary Endpoints:

Efficacy and Safety (Primary):

Primary Efficacy and Safety variables to be evaluated at 30 Days Post Liver Transplant are:

- Incidence of AKI
- Serum creatinine and eGFR

B. Secondary Endpoints:

Efficacy and Safety (Secondary):

Secondary Efficacy and Safety variables to be evaluated at 30 Days Post Liver Transplant are:

- The incidences of acute cellular rejection, (ACR), at 30 days post-transplant.
- Patient survival at 6 months post-transplant.
- Graft survival at 6 months post-transplant.
- Incidence of AEs / SAEs

C. Additional Efficacy and Safety Variables for Evaluation:

- Patient survival at 12 months post-transplant
- Graft survival at 12 months post-transplant

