- Biopsy-proven acute allograft rejection rates at 6 Months and 12 Months post-transplant.
- AKI (Stage 3 rates) at 3 Months post-transplant
- Renal function measured by eGFR at 12 Months post-transplant
- Microbiologically-proven systemic infection rates at 6 Months and 12 Months post-transplant
- Hepatitis C viral loads (in HCV positive recipients) at 12 Months post-transplant
- Incidence of biopsy proven recurrence of HCV infection at 12 Months post-transplant
- Incidence of AEs and SAEs at 12 months post-transplant

For each efficacy event, simple event rate estimates (proportion of events) at 12 months will be obtained, and event rates between the two treatment groups will be compared using Z-statistic based, two-sided, 95% confidence interval for RC – RE, where RC and RE are the event rates for the Early CNI treated Control Group and the Late CNI Initiated/Thymoglobulin® Study Group, respectively. In addition, for the composite efficacy endpoint and its components, individually, Kaplan-Meier survival methods will be used to estimate probabilities of efficacy events by visit. Greenwood’s formula will be used to estimate standard errors and to derive the two-sided, 95% confidence interval of RC – RE, by visit window. HCV replication in HCV positive patients will be compared with summary statistics.

Due to the short duration of study involvement, we expect very few patients to be lost to follow-up, or to withdraw consent. Therefore, for the composite efficacy endpoint, patients who are discontinued from the study for these two reasons, (prior to the incidence of death, graft loss, or biopsy-proven acute cellular rejection), will not be considered as efficacy failures. If there are an adequate number of subjects from each clinical center, a formal test of center by treatment interaction effect will be made.

Adverse Events (AEs) / Infections:

Generally, infections are analyzed together with Adverse Event data. **In addition, infections will be analyzed separately. Infections will be documented on both, the Infection CRF and the AE CRF.** The data collected on both CRFs will be coded with the MedDRA dictionary which gives preferred term and body system information.

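### The primary endpoint is stated in two ways with no rule for which decides the trial, and the 90% power is for change in creatinine at an unstated time point, not for acute kidney injury (AKI)

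*Combined protocol and SAP*

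**What the plan says.** Three places list the primary endpoints: the Study Synopsis, Investigational Plan A, and Study Endpoints A. Each names AKI incidence at 30 days without a stage, and adds "Serum creatinine and eGFR at 30 days post-transplant" or its equivalent. Study Endpoints A introduces its list with "Primary Efficacy and Safety variables to be evaluated at 30 Days Post Liver Transplant are".

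Investigational Plan A then adds, in the singular, "The primary endpoint for the study is a composite renal endpoint of Acute Kidney Injury", restricted to stages 2 to 3 at 30 days. Creatinine and eGFR are not in that sentence. Table 2 below it also defines a stage 1, which can be met on urine output alone: "Less than 0.5 mL/kg per hour for more than 6 hours".

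The primary objective asks whether the delay "reduces the risk/incidence of perioperative acute kidney injury, (AKI), and long-term renal dysfunction". Under Efficacy and Safety Assessments A, "Subjects will be classified for each occurrence of AKI according to the criteria in" Table 2.

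The sample-size text (Investigational Plan C) applies a two-sided 5% level to all tests. It powers a Welch t-test on change in creatinine, with a difference of 0.32 and SDs of 0.51 and 0.12, 0.32 or 0.51. It claims 90% power at 110 patients with a margin for 10% dropout.

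Study Endpoints C says "simple event rate estimates (proportion of events) at 12 months will be obtained". It adds Kaplan-Meier estimates, with a Greenwood confidence interval for the group difference by visit window, for a composite efficacy endpoint. Its later sentence on discontinued patients names two clinical events and, as a third, biopsy-proven rejection: "for the composite efficacy endpoint, patients who are discontinued from the study for these two reasons, (prior to the incidence of death, graft loss".

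**The concern.** Followed as written, the plan does not determine one primary result. Unstaged AKI, stage 2-3 AKI, creatinine and eGFR could each be presented as the planned primary after the data are seen, in an open-label trial, and the documents could not show which was meant.

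The 90% power does not help identify it. It belongs to a change in creatinine, whereas AKI comes first in the objective and in every endpoint list. A null AKI result could be read as strong evidence against an effect because the trial claims 90% power, although that figure was never calculated for AKI.

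**Working it through.** **1. The endpoint statements side by side**

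| Place | AKI | Creatinine, eGFR | Time |
|---|---|---|---|
| Synopsis; Plan A list; Study Endpoints A | no stage | primary | 30 days |
| Plan A, sentence before Table 2 | stages 2-3 | not named | 30 days |
| Study Endpoints C, simple rates | not specified | not applicable | 12 months |
| Study Endpoints C, Kaplan-Meier | undefined composite | not applicable | by visit window |

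The 5% two-sided level is stated per test. No hierarchy, all-or-any rule or alpha split appears anywhere.

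**2. The plan's own power figure**

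The method is Welch's t with the noncentral t distribution and λ = 0.32 / √(SD1²/n1 + SD2²/n2).
- SDs 0.51 and 0.51, 55 per arm: λ = 0.32 / √(2 × 0.2601/55) = 3.29, df 108, power 90.3%. The plan's 110 is reproduced. All twelve entries of the sample-size table also reproduce (46/60, 58/78, 82/110; 16/20, 18/22, 20/26).
- With 10% dropout, 110 × 0.9 = 99 evaluable (50 and 49). SDs 0.51 and 0.51: λ = 3.12, power 87.1%.
- The same 99 with SDs 0.51 and 0.32: λ = 0.32 / √(0.2601/50 + 0.1024/49) = 3.75, power 95.9%.

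The 110 matches the row with both SDs 0.51, before dropout. The claimed dropout margin fits the 0.32 row, which needs 78, or about 86 after the plan's own 10% increase. The text mentions 0.32 in parentheses, but 0.32 is both the difference and the middle SD, so the design row cannot be identified.

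**3. Time point of the powered variable**

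The GFR row is labelled Month 12; the creatinine row has no label. The dropout sentence refers to 12-month values, which makes Month 12 possible for creatinine but does not establish it.

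**4. Power for stage 2-3 AKI (illustration only)**

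The documents give no design values. Power is the sum of binomial probabilities over all outcomes with |z| > 1.96, with 55 per arm and z = (x − y)/55 / √(2p̄(1 − p̄)/55).

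| Control risk | Source | Halved | Cut by one third |
|---|---|---|---|
| 20% | assumed | 31% | 15% |
| 36.8% | 11.1% + 25.7%, Introduction B, taken as exclusive categories | 59% | 29% |
| 46% | another cohort in Introduction B: creatinine above 2.0 mg/dL or renal replacement | 74% | 39% |
| 60% | assumed | 89% | 54% |

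The 36.8% risk is unrelated to the GFR difference of 36.8 in the sample-size table.

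**5. Type I error if any one of three tests counted (illustration only)**

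The documents do not state this rule. The three statistics (AKI, creatinine, eGFR) are simulated as trivariate normal, each tested at two-sided 5%. The assumed correlations are 0.7 to 0.98 between creatinine and eGFR and 0.3 to 0.7 between AKI and each of them. The chance of at least one false positive runs from 9.1% (0.98 and 0.7) to 12.5% (0.7 and 0.3). On the single-endpoint reading it is 5%; if all must succeed, it is at most 5%.

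**The case against.** The strongest defence is that the stage 2-3 sentence simply defines the AKI bullet above it, so there is only one AKI endpoint. That is a fair reading of the one section. But the sentence still names one endpoint where the lists name three variables, and the dedicated endpoint section repeats the unstaged list. The word incidence, and the classification of every occurrence, also lean towards cumulative AKI through Day 30, though no sentence says so.

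Second, the by-visit Kaplan-Meier interval could supply a Month 1 comparison, since Month 1 is a scheduled visit and the only endpoint the protocol itself calls a composite is the renal one. This is a real possibility, so a reader should not infer that the plan offers only 12-month comparisons. It stays unresolved because the composite is undefined and is next discussed with death, graft loss and rejection.

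Third, creatinine is a listed primary, so the trial is powered for something on the list. This stands in part. However, the list gives creatinine at 30 days without calling it a change, and the powered change has no time point.

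Fourth, in a Phase 2 trial AKI power is a matter of disclosure. I accept that. The need to identify one primary result is stronger, because the hypothesis is superiority and 90% power is claimed.

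**Conclusion.** The point holds. The governing primary endpoint and success rule are missing and must be settled before outcome data are seen. The 90% power applies to neither AKI version, and its time point and SD row are unstated: 87% or 96% with 99 evaluable, depending on the row. These conclusions rest on the text and the plan's own inputs.

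Four stronger readings are not supported:
- **The type I error is inflated.** The 9% to 12.5% needs an any-one-wins rule that the documents do not contain, and it rests on assumed correlations.
- **The trial is underpowered for AKI.** The 31% to 89% and 15% to 54% ranges rest on assumed reductions and on control risks that are assumed or borrowed from other cohorts and definitions. They do not extend to unstaged AKI, whose control risk may be quite different.
- **The power calculation is for Month 12 creatinine.** That is possible, but not stated.
- **The sample-size arithmetic is wrong.** Every table entry reproduces. The fault is in what the calculation is attached to.

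**What to change.** **1. Endpoint.** Before outcome data are seen, name one governing primary endpoint and make the Synopsis, Investigational Plan A, and Study Endpoints A and C agree.
- If stage 2-3 AKI is kept, which is the protocol's own single-endpoint sentence, say whether it is cumulative through Day 30 or status at Day 30. State its Day-30 test at two-sided 5%. Make Day-30 creatinine and eGFR secondary, or test them in sequence after AKI.
- If creatinine is chosen, state its time point and whether it is a change from baseline.
- If several primaries stay, state the success rule and the alpha split.
- In Study Endpoints C, define or remove the composite efficacy endpoint, and separate the Day-30 comparison from the 12-month rates.

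**2. Power statement.** Replace it in Investigational Plan C with text such as: *Power refers to change in creatinine at [time point]. With 110 evaluable and both SDs 0.51 it is 90%. With 10% dropout (99 evaluable) it is 87% if both SDs are 0.51 and 96% if the second SD is 0.32. The design basis was [row]. No AKI effect was assumed.* If stage 2-3 AKI is primary, add its power range, labelled illustrative.

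**Cost.** No extra patients: one decision and matching edits. The stated power may look less favourable. Under sequential testing, creatinine goes formally untested whenever AKI is not significant. For a halving, that is 100% minus the power above: 69%, 41%, 26% and 11% of the time across the four control risks. If creatinine becomes primary, AKI, which the objective names first, becomes secondary.

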Acute Kidney Injury (AKI): Rapid decline in renal function with or without the need for renal replacement therapy is common in the period immediately before and after liver transplantation.^{1-4, 21-24} In a series of 105 OLT recipients, McCauley et al showed that 94.3% of recipients had acute renal failure defined as a 50% increase from the baseline preoperative serum creatinine.⁴ In addition, 10% of recipients in the McCauley series from Pittsburgh required renal replacement therapy (RRT) in the form of CVVHD or intermittent hemodialysis.⁴ In a Spanish series, Gainza et al found acute renal failure, (serum creatinine >2.0 mg/dL or need for RRT), in 46% of OLT recipients in the postoperative period.²³ Series from Mount Sinai Medical Center, New York and Baylor College of Medicine, Dallas found a postoperative RRT rate of 22% and 12% respectively in relatively large cohorts, (n = 1602 and 724), of OLT recipients.^{22, 24} Large differences in the reported rates of postoperative acute renal failure is partly due to the lack of use of a standard definition of acute renal failure of which there was none until 2004.^{25, 26}

O’Riordan employed the RIFLE criteria²⁵ for the definition of acute renal failure in a study of 359 OLT recipients in Ireland, and found an 11.1% postoperative incidence of 2-fold increase in serum creatinine and a 25.7% incidence of 3-fold postoperative increase in serum creatinine, or the need for RRT.² Most studies consistently show that postoperative renal failure had a significant impact on post transplant outcomes, including mortality.^{1-4, 21-24}

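### Table 2 gives the Stage 1 and Stage 2 creatinine bands as percentage increases that contradict the fold values beside them, at the cut-off for an AKI primary event

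*Combined protocol and SAP*

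**What the plan says.** Investigational Plan, section A (Overall Study Design), states: "The primary endpoint for the study is a composite renal endpoint of Acute Kidney Injury". It limits this to stages 2 to 3 at 30 days and refers to Table 2 for the staging, which it attributes to the AKIN system. Efficacy and Safety Assessments, section A (Renal function), makes the same table operative: "Subjects will be classified for each occurrence of AKI according to the criteria in" Table 2.

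The creatinine column of Table 2 has three rows, each with a percentage and a bracketed fold value:

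- Stage 1: a rise of at least 0.3 mg/dL, or an increase *of* 150% to 200%, with the bracket ending "1.5 to 2-fold), from baseline".
- Stage 2: "Increase in serum creatinine of $> 200\%$ to 300% , (>2 to 3-fold), from baseline".
- Stage 3: "Increase in serum creatinine to more than 300% , (>3 -fold), from baseline", or creatinine of at least 4 mg/dL with an acute rise of at least 0.5 mg/dL.

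Each stage also has a urine-output criterion. The footnote says that one criterion is enough and that any renal replacement therapy counts as Stage 3.

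**The concern.** An increase *of* X% and an increase *to* X% differ by one full multiple of baseline. Stages 1 and 2 use the first form and Stage 3 the second, although all three fold values follow the second. Two cells therefore each state two incompatible bands.

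The Stage 1/Stage 2 boundary is the boundary between a non-event and a primary AKI event. Someone who computes percent change from baseline and compares it with the printed percentages gets a different event set from someone who computes the ratio and uses the bracketed fold. No section of the plan says which half of the cell governs, and no derivation rule for the stage is given. The literal sense of a percentage increase is also ordinary usage in this protocol: Introduction, section B, describes a published series with "acute renal failure defined as a 50% increase from the baseline preoperative serum creatinine", which means 1.5 times baseline.

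**Working it through.** **Inputs.** The percentage bands, fold bands, 0.3 mg/dL route, 4 mg/dL route and one-criterion rule all come from Table 2 and its footnote.

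**Formulas.** Increase *to* X% of baseline: fold = X/100. Increase *of* X%: fold = 1 + X/100.

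| Row | Printed percentage | Fold if *to* | Fold if *of* | Printed fold |
|---|---|---|---|---|
| Stage 1 | 150% to 200% | 1.5 to 2.0 | 2.5 to 3.0 | 1.5 to 2 |
| Stage 2 | >200% to 300% | >2.0 to 3.0 | >3.0 to 4.0 | >2 to 3 |
| Stage 3 | >300% | >3.0 | >4.0 | >3 |

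The printed fold values are reproduced in every row by *to*, and in no row by *of*. With *to* throughout, the ratio bands meet without gap or overlap.

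**Literal reading, row by row as printed.** Stage 2 is >3.0 to 4.0 times baseline and Stage 3 is >3.0 times. The Stage 2 ratio band lies wholly inside Stage 3 and adds nobody. If Stage 3 were also read as *of*, Stage 2 would become a separate band, but the lowest ratio that counts as an event would still be just above 3.

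**Test records (mg/dL), creatinine criteria only:**

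| Baseline to later value | Ratio | Stage by fold | Stage by literal wording |
|---|---|---|---|
| 0.8 to 1.68 | 2.1 | 2 | 1 |
| 1.0 to 2.5 | 2.5 | 2 | 1 |
| 1.2 to 3.48 | 2.9 | 2 | 1 |
| 1.5 to 4.05 | 2.7 | 3 | 3 |
| 2.0 to 4.4 | 2.2 | 3 | 3 |
| 1.0 to 3.2 | 3.2 | 3 | 3 |

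The first three fall to Stage 1 because their rises (0.88, 1.5 and 2.28 mg/dL) exceed 0.3 mg/dL while their percentage increases (110%, 150% and 190%) do not exceed 200%.

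**Reach of the 4 mg/dL route.** A ratio of at most 3 can reach 4 mg/dL only if baseline is at least 4/3 = 1.33 mg/dL. Every ratio above 2 exceeds 4 mg/dL once baseline is at least 4/2 = 2.0 mg/dL. Below 1.33 mg/dL this route retains nobody in the >2- to 3-fold band. From 1.33 to 2.0 mg/dL it retains some, and from 2.0 mg/dL all.

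**Other routes.** Urine output below 0.5 mL/kg/h for more than 12 hours, the Stage 3 urine criterion and renal replacement therapy also keep a patient in the endpoint. Appendix A schedules no urine-output assessment, so this route may retain few; the documents give nothing to size it.

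**Sample size.** Investigational Plan, section C, powers the trial on delta creatinine. A Welch t-test with difference 0.32, both standard deviations 0.51 and two-sided 5% gives totals of 82 (80% power) and 110 (90% power), as printed. Nothing in that calculation comes from Table 2.

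**The case against.** The strongest reply is that the table corrects itself. Every row prints the multiple of baseline, the multiples agree with the Stage 3 wording, and the literal reading makes Stage 2 redundant on creatinine, so a careful reader sees at once that it was not meant. The plan also names AKIN as the governing system. The cited source is not available here, so whether the wording was carried over from it cannot be judged. Serum creatinine must be recorded on the visit form, data go into one REDCap database with central monitoring, and no section says that sites assign the stage. Any misclassification could therefore be corrected from the stored values. The 50% example in the Introduction describes someone else's series and sets no convention for Table 2.

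All of this stands, and it limits the severity. It does not remove the contradiction: the cell that sets the event threshold still states two thresholds, with no rule for choosing between them.

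A reader might also infer two stronger claims, and neither is supported.

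- *Every patient with a >2- to 3-fold rise leaves the endpoint.* This is false: the 4 mg/dL, urine-output and renal replacement routes retain some, as the 1.5 to 4.05 and 2.0 to 4.4 mg/dL records show.
- *The loss can be sized from the Irish series in the Introduction.* There, 11.1% had a 2-fold rise and 25.7% a 3-fold rise or renal replacement, which suggests 11.1 + 25.7 = 36.8% against 25.7%, or 11.1/36.8 = 30% of events lost. That series was classified by RIFLE, in another population. The figure counts all 11.1 points as lost despite the other routes, and it supposes that the whole trial adopts the unintended reading. A power loss built on it would also need an AKI risk ratio, which the plan does not give.

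**Conclusion.** The concern holds in a limited form. The Stage 1 and Stage 2 percentages in Table 2 are wrong as worded: each sits one full multiple of baseline above the fold value in its own cell and is inconsistent with the Stage 3 wording. Applied literally, they move the creatinine-ratio cut-off for an AKI primary event from >2-fold to >3-fold, and patients who qualify only on a >2- to 3-fold ratio would be scored Stage 1.

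How many patients that is cannot be computed, because the documents give no distribution of creatinine ratios or baselines for this population under these bands. Whether anyone would apply the literal reading is also unknown. The fold text shows the intended rule. The sample size is unaffected, and so are the 30-day serum creatinine and eGFR endpoints, which do not use the staging. With each row read as printed, Stage 3 membership does not change either. This is a cheap correction worth making because of where the error sits, not evidence that the endpoint is unusable.

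**What to change.** In the Stage 1 and Stage 2 rows of Table 2, change *of* to *to* for the percentage bands. Alternatively, drop the percentages and state multiples of baseline only: Stage 1, 1.5 to 2.0; Stage 2, >2.0 to 3.0; Stage 3, >3.0. Leave the 0.3 mg/dL, 4 mg/dL, urine-output and renal replacement routes unchanged. State that the creatinine stage is derived by program from the recorded baseline and post-transplant values using these multiples, so that one cut-off applies at all four centres.

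The cost is a rewording of two table cells and a few lines of derivation code. No extra patients, visits or measurements are needed.
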